11.4 ELECTROCARDIOGRAM

Descriptive statistics for ECG parameters (ie, heart rate, PR interval, QRS interval, QT interval, and QTc interval) at baseline, postbaseline, and changes from baseline values at each postbaseline timepoint will be presented.

ECG parameter values are considered PCS if ECG values meet either the actual value or change from baseline PCS high criteria listed in [Table 11-4](#). The number and percentage of participants with PCS postbaseline values will be tabulated. The percentages will be calculated relative to the number of participants with an available non-PCS baseline value and at least 1 postbaseline assessment. The numerator will be the total number of participants with an available non-PCS baseline value and at least 1 PCS postbaseline ECG value during the study. A supportive listing of participants with PCS postbaseline values will be provided. A listing of all AEs for participants with PCS ECG values will also be provided.

To evaluate ECG postbaseline values of clinical interest, the number and percentage of participants with post-treatment QTcF >450 ms, >480 ms, or >500 ms will be tabulated by treatment group. A supportive listing of participants with postbaseline clinical interest will be provided. A listing of all AEs for participants with postbaseline clinical interest will also be provided.

The number and percentage of participants with an increase > 30 msec but ≤ 60 msec, and with an increase > 60 msec in QTcF will be tabulated. Participants will be counted only once for the most severe category. A supportive listing of participants with postbaseline QTcF increases > 30 msec will be provided, including the PID number, study center, and all QTc values (including changes from baseline). A listing of all AEs for participants with postbaseline QTcF increases > 30 msec will also be provided.

A shift table from baseline to the end of open-label treatment period in the investigator's overall interpretation of the ECG will be presented for the following categories: normal; abnormal, not clinically significant; abnormal, clinically significant. A tabular display of participants with postbaseline clinically significant ECG abnormalities according to the investigator's overall interpretation will be provided.

Table 11-4 Criteria for Potentially Clinically Significant Electrocardiograms

Parameter	Unit	Criterion
QRS interval	msec	≥ 150
PR interval	msec	≥ 250
QTc (QTcB or QTcF) interval	msec	> 500
QTc (QTcB or QTcF) interval	msec	Increase from baseline > 60

QTc = QT interval corrected for heart rate.

QTcB = QT interval corrected for heart rate using the Bazett formula.

QTcF = QT interval corrected for heart rate using the Fridericia formula.

11.5 COLUMBIA-SUICIDE SEVERITY RATING SCALE

For C-SSRS, the number and percentage of participants with suicidal ideation or suicidal behavior as recorded on the C-SSRS will be summarized for the Safety Population. The distribution of responses for most severe suicidal ideation and most severe suicidal behavior in the participant's lifetime history, in the open-label treatment period, and in the safety follow-up period will also be presented. Supportive listings will be provided and will include the PID number, study center number, lifetime history, and postbaseline values. Intensity of suicidal ideation and suicidal behavior type will also be included in these listings.

12.0 COVID-19 RELATED ANALYSES

This section specifies analyses related to COVID-19 pandemic from the following aspects:

- Disposition
- Study visits and study procedures
- Protocol deviation
- Treatment interruption due to COVID-19
- TEAEs related with COVID-19 and supplemental signs and symptoms
- COVID-19 status (COVID-19 testing results or contact with a COVID-19 positive person)

Safety population will be used for the planned analyses described above. The number of participants impacted by COVID-19 will be summarized. In addition, the number of participants impacted by COVID-19 and their corresponding disposition status in the open-label treatment period and the follow-up period will be tabulated, respectively.

The number of participants with study visits impacted by COVID-19 will be summarized by the classification of study visits (missed, clinical visits in person, remote [auto/video]).

Furthermore, the number of participants who missed at least one entire visit due to COVID-19 will be summarized; the number of participants who missed at least one assessment due to COVID-19 will be summarized by assessment procedures (laboratory, C-SSRS, urine pregnancy test, vital signs and ECG) and visit. The number of participants with remote assessments of C-SSRS and pregnancy test will be summarized by visit.

The number of participants with significant protocol deviation due to COVID-19 will be provided. The number of participants with study drug disruption due to COVID-19 will be provided as well. The number of participants with TEAEs related to COVID-19 will be tabulated by preferred terms, and related supplemental signs and symptoms will be listed. COVID-19 status, i.e., testing results or contact with a COVID-19 positive person, will be summarized.

Supporting listings for the described analyses above will be provided.

13.0 HEALTH OUTCOMES ANALYSES

Not Applicable.

14.0 SUBGROUP ANALYSES

No subgroup analysis is planned.

15.0 **INTERIM ANALYSIS**

Interim data-cuts are planned to provide ongoing safety data to support global regulatory submissions.

16.0 DETERMINATION OF SAMPLE SIZE

As this is a safety extension study from the lead-in Study 3101-301-002, all participants from the lead-in study who are eligible for this extension study will be enrolled. No separate sample size calculation was performed. Based on expected completion rate from the lead-in Study 3101-301-002, approximately 750 participants will be enrolled into this long-term, open-label, safety extension study.

17.0 STATISTICAL SOFTWARE

Statistical analyses will be performed using version 9.4 or newer of SAS.

18.0 DATA HANDLING CONVENTIONS

18.1 VISIT TIME WINDOWS

The analysis visit windows for safety endpoints are defined as follows:

Table 18.1–1. Safety Analysis Visit Definitions

Analysis Visit (Derived)	Scheduled Visit Day^a	Window
Baseline		Baseline from lead-in study
Week 4	Day 28 (Visit 2)	Treatment Day [1, 42]
Week 8	Day 56 (Visit 3)	Treatment Day [43, 70]
Week 12	Day 84 (Visit 4)	Treatment Day [71, 98]
Week 16	Day 112 (Visit 5)	Treatment Day [99, 126]
Week 20	Day 140 (Visit 6)	Treatment Day [127, 154]
Week 24	Day 168 (Visit 7)	Treatment Day [155, 182]
Week 28	Day 196 (Visit 8)	Treatment Day [183, 210]
Week 32	Day 224 (Visit 9)	Treatment Day [211, 238]
Week 36	Day 252 (Visit 10)	Treatment Day [239, 266]
Week 40	Day 280 (Visit 11)	Treatment Day [267, the last open-label visit]
End of open-label treatment period		Last available assessment during open-label treatment period
Safety Follow-up/EOS	Day 308 (Visit 12)	Treatment Day [the last open-label visit +1, the last study visit]
End of Study		Last available assessment Day after treatment start date, i.e. occurs at final visit (expected Day 280) or ET

^a Relative to the date of the first dose of study treatment. Day 1 = the date of the first dose of study treatment. There is no Day 0 or Week 0.

End of Treatment is defined as the last available assessment during open-label treatment period, i.e. on or before the treatment end date. End of Treatment results will be presented in analysis tables for clinical laboratory values, electrocardiogram and vital signs.

End of Study is defined as the last available assessment during the study, including open-label and safety follow-up period. End of Study results will be presented in analysis tables for safety parameters, including but not limited to electrocardiograms, clinical laboratory values, and vital signs.

ET = early termination. EOS=end of study.

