**Table 2. Schedule of Visits and Procedures for Visits Conducted Remotely Due to the COVID-19 Pandemic**

Study Period	Open-label Treatment Period (40 weeks) a										Safety Follow-up Period (4 weeks)
	Visit #	Visit 2	Visit 3	Visit 4	Visit 5	Visit 6	Visit 7	Visit 8	Visit 9	Visit 10	
Day/Week	Week 4 (Day 28)	Week 8 (Day 56)	Week 12 (Day 84)	Week 16 (Day 112)	Week 20 (Day 140)	Week 24 (Day 168)	Week 28 (Day 196)	Week 32 (Day 224)	Week 36 (Day 252)	Week 40 (Day 280)	Week 44 (Day 308)
Visit Windows	± 3 days	± 3 days	± 3 days	± 3 days	± 3 days	± 3 days	± 3 days	± 3 days	± 3 days	± 3 days	± 3 days
Access IWRS	X	X	X	X	X	X	X	X	X	X	X
Provide urine pregnancy test and instructions b	X	X	X	X	X	X	X	X	X	X	X
C-SSRS	X	X	X	X	X	X	X	X	X	X	X
Dispense study intervention (ie, atogepant)	X	X	X	X	X	X	X	X	X	X	X
Review of study intervention (ie, atogepant)	X	X	X	X	X	X	X	X	X	X	X
Compliance and accountability	X	X	X	X	X	X	X	X	X	X	X
Adverse Events											
Concomitant medications/concurrent procedures	X	X	X	X	X	X	X	X	X	X	X

C-SSRS = Columbia Suicide Severity Rating Scale; ECG = electrocardiogram; EOS = end of study; IWRS = interactive web response system.

a For participants who have a study visit replaced by a remote study visit, all missed in-person safety assessments (clinical laboratory determinations, vital signs, and ECGs) will be collected at the next in-person visit. To ensure participant safety, remote study visits can be performed for up to 8 weeks at the discretion of the investigator, after which, participants who cannot attend in-person for a study visit must be discontinued from the study.

b For women of childbearing potential only, a urine pregnancy test must be performed within 48 hours prior to the remote visits. Investigators/site staff will provide participants with study-supplied urine pregnancy tests and corresponding written instructions to be used at home by participants for remote study visits. Sites are required to verbally review testing instructions with all participants.

c During the COVID-19 pandemic, Visit 12 (Follow-up/End of Study) should be conducted remotely for all participants.

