### 8.4.1 Open-label Treatment Period (40 Weeks)

#### 8.4.1.1 Visit 1 (Day 1)

- Obtain informed consent and participant privacy.
- Register participant in IWRS.
- Review and record prior medications taken in the past 6 months, and all prior migraine headache medications and concomitant medications.
- Assess inclusion/exclusion criteria.
- Assess C-SSRS (the “Since Last Visit” assessment of the C-SSRS will be completed).
- Collect vital sign measurements (sitting and standing systolic and diastolic BP, pulse rate, respiration rate, temperature, and weight).
- Perform physical examination.
- Perform urine pregnancy test for women of child-bearing potential.
- Collect urine for drug screen.
- Perform and transmit ECG
- Collect blood and urine for clinical laboratory determinations including: serology, INR, and urinalysis.
- Review and assess AEs.
- Review and update concomitant medications and concurrent procedures.

- Access IWRs and obtain the kit number for atogepant bottle and dispense atogepant bottle.

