#### **8.4.1.2 Visits 2 to Visit 11 (Week 4 to 40)**

Refer to [Table 2](#) for assessments to be performed at study visits conducted remotely due to the COVID-19 pandemic.

- Perform urine pregnancy test for women of child-bearing potential.
- Collect vital sign measurements (sitting and standing systolic and diastolic BP, pulse rate, respiration rate, temperature, and weight).
- Collect blood and urine samples for chemistry, hematology, INR, and urinalysis.
- Assess C-SSRS (the “Since Last Visit” assessment of the C-SSRS will be completed).
- Perform and transmit ECG (Visit 4 [Week 12], Visit 7 [Week 24], and Visit 11 [Week 40] only).
- Collect previous visit atogepant bottle, review participant compliance and perform accountability.
- Review and assess AEs.
- Review and update concomitant medications and concurrent procedures.
- Access IWRs to dispense atogepant bottle and enter accountability.

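### The SAP's 4-weekly visit windows do not fit the ECG schedule: a pre-dose Visit 1 ECG can be labelled Week 4, and make-up ECGs leave the Week 12 and Week 24 rows

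*SAP*

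**What the plan says.** SAP 18.1 introduces its window table with "The analysis visit windows for safety endpoints are defined as follows" and gives a single set; no ECG-specific set appears. The Week 4 row is "Treatment Day [1, 42" and the Week 16 row is "Treatment Day [99, 126". The footnote fixes the day count: "Day 1 = the date of the first dose of study treatment. There is no Day 0 or Week 0".

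Protocol 8.4.1.1 lists "Perform and transmit ECG" among the Visit 1 (Day 1) procedures. For later visits, Protocol 8.4.1.2 says "Perform and transmit ECG (Visit 4 [Week 12], Visit 7 [Week 24], and Visit 11 [Week 40] only". Footnote a of Protocol Table 2 says that ECGs and other in-person assessments missed at a remote visit "will be collected at the next in-person visit".

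For ECG parameters, SAP 11.4 says that "changes from baseline values at each postbaseline timepoint will be presented". SAP 11.0 and 18.3 take baseline from before the first lead-in dose, so a Visit 1 ECG counts as post-baseline. SAP 18.3 uses all post-baseline assessments for PCS determinations. Its only selection rule for repeated or unscheduled assessments concerns the end-of-study value.

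**The concern.** Windows 28 days wide suit laboratory tests and vital signs, which are collected every 4 weeks. After Visit 1, ECGs are 84 days apart (Day 84 to Day 168) and then 112 days apart (Day 168 to Day 280). Applied to ECGs, the windows create labels with no scheduled tracing behind them, and they close too early to hold a make-up taken at the next scheduled visit.

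What is at stake is how the by-visit QTc and change-from-baseline table reads. A Visit 1 tracing reflects the lead-in treatment (placebo, 10, 30 or 60 mg), or time off treatment for participants who entered at or after lead-in Visit 8. Under a Week 4 label it would look like a result after 4 weeks of open-label 60 mg. The Week 12 and Week 24 rows would also be short of participants whose visits were remote, and those participants would appear in small rows elsewhere.

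**Working it through.** **Inputs.** Windows and day numbering come from SAP Table 18.1-1. The ECG schedule comes from the text of Protocol 8.4.1.1 and 8.4.1.2, because the schedule tables did not extract cleanly. The visit tolerance of ±3 days is in the protocol's schedule tables. The make-up rule and the 8-week limit on remote visits are in Protocol 8.4 and Table 2.

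**Reproducing the SAP windows.** With visits at Day 28k, splitting at the midpoints gives [28k − 13, 28k + 14]. For Week 16, k = 4: 112 − 13 = 99 and 112 + 14 = 126, which is the stated row. The rule reproduces every row from Week 8 to Week 36. Two end rows differ. Week 4 would be [15, 42] but is set at [1, 42], and Week 40 runs from Day 267 to the last open-label visit.

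**Placing the ECGs.**

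| ECG | Treatment days | SAP row |
|---|---|---|
| Visit 1, first dose the same day | 1 | Week 4 [1, 42] |
| Week 12, on time | 81-87 | Week 12 [71, 98] |
| Week 12, one visit late | 109-115 | Week 16 [99, 126] |
| Week 12, two visits late | 137-143 | Week 20 [127, 154] |
| Week 24, on time | 165-171 | Week 24 [155, 182] |
| Week 24, one visit late | 193-199 | Week 28 [183, 210] |
| Week 24, two visits late | 221-227 | Week 32 [211, 238] |
| Week 40, on time | 277-283 | Week 40 [267, last open-label visit] |

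The Week 12 and Week 24 windows close 14 days after target (98 − 84 and 182 − 168). The next scheduled visit is 28 days after target, or 25 at the early edge of its tolerance, so a make-up at a scheduled visit cannot fall back into either row. Whether a make-up can come two visits late depends on how the 8-week limit is read. Week 40 is largely protected because its window is open-ended.

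**Checking ECG-specific windows.** The midpoints between scheduled ECGs are (84 + 168)/2 = 126 and (168 + 280)/2 = 224. This gives Week 12 = [2, 126], Week 24 = [127, 224] and Week 40 = [225, last open-label visit]. Make-ups one visit late return to their own row: Days 109-115 to Week 12 and Days 193-199 to Week 24. Make-ups two visits late do not all return: Days 137-143 go to Week 24, and Days 221-227 straddle Weeks 24 and 40.

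**The case against.** The strongest reply is that a Day 112 tracing really is a Week 16 observation, and that windowing by actual treatment day is a legitimate choice. That stands: the make-up is correctly timed. What remains is that the Week 12 and Week 24 rows lose those participants to rows where no ECG was planned. The reply does not rescue the Visit 1 ECG, which is pre-dose and is not a Week 4 observation in any sense.

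The Week 4 effect is conditional. The amended protocol calls Visit 1 Day 1 but no longer says where the first dose is taken. If dosing starts a day later, the Visit 1 ECG precedes Day 1 and falls in no window. For direct rollovers, lead-in Visit 7 procedures are not repeated, and the SAP does not say whether that ECG enters the extension dataset.

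A reader might infer that seven of the ten open-label rows (Weeks 4, 8, 16, 20, 28, 32 and 36) would print with no scheduled ECG behind them. The documents do not establish that. Table specifications are in a separate document (SAP 4.0), and make-ups at scheduled visits reach only Weeks 16, 20, 28 and 32. If the specifications suppress the unscheduled rows, though, the ECGs concerned drop out of the by-visit summary and are not put back where they belong.

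A reader might also infer that every remote Visit 4 or Visit 7 participant is lost from those rows. Protocol 8.6 allows unscheduled visits, and an in-person ECG by Day 98 or Day 182 stays in its row. SAP 12.0 also counts assessments missed because of COVID-19 by procedure, ECG included, and by visit. Thin rows would be partly explained, though not refilled.

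Finally, the SAP change log says the windows were revised to ease ISS preparation. That is a reason to coordinate a change, but it does not make the Day 1 start suitable for ECGs.

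**Conclusion.** The point holds as a mismatch between a stated rule and the ECG schedule, confined to by-visit descriptive ECG statistics. Followed literally, Table 18.1-1 puts a Day 1 pre-dose ECG in Week 4. It moves make-ups from Week 12 to Week 16 or 20, and from Week 24 to Week 28 or 32. The first effect assumes the first open-label dose on the Visit 1 date and the Visit 1 ECG in the extension dataset. The second assumes the make-up is done at a later scheduled visit. The documents do not give the number of participants affected.

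It would be wrong to conclude that safety findings are lost. PCS counts use all post-baseline values. The QTcF threshold and increase categories in SAP 11.4 are not tied to visit windows. End of Treatment and End of Study take the last available value. The point is worth correcting because safety is the study's only objective and a planned table would otherwise be mislabelled or incomplete, but it does not threaten the main safety counts.

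**What to change.** Make two edits to SAP Table 18.1-1.

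1. Keep pre-dose Visit 1 assessments out of the on-treatment by-visit rows, either by starting the Week 4 window at Day 2 or by showing Visit 1 as its own row. State whether a lead-in Visit 7 ECG that serves as the Visit 1 ECG is included.
2. Add ECG windows: Week 12 = Days 2-126, Week 24 = Days 127-224, Week 40 = Day 225 to the last open-label visit. Where a window holds more than one ECG, use the one closest to the target day.

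Leave the SAP 18.3 rule unchanged, so that all post-baseline ECGs, Visit 1 included, still count for PCS.

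The cost is a table edit and minor programming, with no new data. There are three downsides. Early-termination ECGs fall into wider windows, so a very early one would be labelled Week 12. Make-ups two visits late (Days 137-143 and 221-227) are not fully returned to their intended row; one that lands in a row with an on-time ECG would be passed over under the closest-to-target rule. The ISS windows may need to be aligned.

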## 8.8 Early Discontinuation of Participants

A premature discontinuation will occur when a participant who signed the ICF ceases participation in the study, regardless of circumstances, before completion of the study.

Participants can be prematurely discontinued from the study for one of the following reasons:

- AE
- Lack of efficacy
- Lost to follow-up
- Non-compliance with study intervention (ie, atogepant)
- Pregnancy
- Protocol deviation
- Site terminated by Allergan
- Study terminated by Allergan
- Withdrawal by participant

Participants may voluntarily withdraw from the study at any time.

Notification of early participant discontinuation from the study and the reason for discontinuation will be made to the sponsor and will be clearly documented on the appropriate eCRF. All participants who prematurely discontinue from the study, regardless of cause, should

be seen for final study assessments. The final assessments will be defined as the evaluations scheduled for Visit 11/ET and Visit 12/EOS, 4 weeks post the last dose of atogepant.

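### As written, the SAP's Week 4 to Week 36 windows overlap the Safety Follow-up row for early terminators, and no rule says which row takes an off-drug value

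*SAP*

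**What the plan says.** SAP 18.1, Table 18.1-1, gives each week from 4 to 36 a fixed range with no other condition: Week 4 is "Treatment Day [1, 42", Week 12 is "Treatment Day [71, 98", Week 20 is "Treatment Day [127, 154" and Week 36 is "Treatment Day [239, 266" (each range is closed at its upper day). Week 40 is different: "Treatment Day [267, the last open-label visit". Safety Follow-up/EOS is "Treatment Day [the last open-label visit +1, the last study visit", with no minimum day.

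The table's footnote defines the day count: "Relative to the date of the first dose of study treatment. Day 1 = the date of the first dose of study treatment". It does not stop at the last dose. A limit at the treatment end date is stated for End of Treatment only. SAP 18.3 covers the end-of-study assessment and PCS determination. It gives no order between rows and no choice between two values in one weekly window.

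Protocol 8.8 says that participants who stop early should still be seen at the end: "The final assessments will be defined as the evaluations scheduled for Visit 11/ET and Visit 12/EOS, 4 weeks post the last dose of atogepant". Protocol 8.4.2.2 lists vital signs, chemistry, hematology, INR and urinalysis at an in-person Visit 12, but no ECG. During the pandemic Visit 12 is remote (Protocol 8.4.2.1), and the remote schedule in Protocol Table 2 has neither laboratory tests nor vital signs.

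**The concern.** For a completer the rows are disjoint. For someone who stops early, the follow-up row begins inside the span of Days 1 to 266 that the fixed weekly rows already cover without a gap. Read literally, an in-person Visit 12 measurement about four weeks off drug qualifies for a weekly row and for Safety Follow-up/EOS. So does a repeat or unscheduled sample taken after ET, such as the serial chemistry that Protocol 9.5 asks for after a confirmed ALT or AST elevation.

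SAP 11.2 and 11.3 plan values and changes from baseline at each postbaseline timepoint. Off-drug values, all from early stoppers, could enter rows that a reader takes as on-treatment, and one measurement could appear twice. Two programmers following the SAP could produce different tables.

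**Working it through.** **Reproducing the windows.** For Weeks 8 to 36 the range is scheduled day − 13 to scheduled day + 14. For example, Week 20 is 140 − 13 = 127 to 140 + 14 = 154. Week 4 is the same, except that it starts at Day 1 and ends at 28 + 14 = 42. All nine stated ranges are reproduced.

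**Mapping Visit 12.** Base case: the ET visit is on the last-dose day d, and Visit 12 is on day d + 28. Each pair is tested against the rows as written.

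| ET day | Visit 12 day | Weekly row met | Safety Follow-up row |
|---|---|---|---|
| 7 | 35 | Week 4 [1, 42] | [8, 35], met |
| 60 | 88 | Week 12 [71, 98] | [61, 88], met |
| 100 | 128 | Week 20 [127, 154] | [101, 128], met |
| 238 | 266 | Week 36 [239, 266] | [239, 266], met |
| 239 | 267 | none (Week 40 is capped) | [240, 267], met |
| 280 | 308 | none | [281, 308], met |

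The overlap requires d + 28 ≤ 266, so d ≤ 238. Every ET day from 1 to 238 gives a double match. For d + 28 ≤ 42, that is d ≤ 14, the ET and Visit 12 values both lie in Week 4.

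**Sensitivity to timing.** With Visit 12 at 25 or 31 days (the ±3-day visit window), the last affected ET day is 266 − 25 = 241 or 266 − 31 = 235. If the ET visit is 7 or 14 days after the last dose, and Visit 12 stays 28 days after the last dose, the affected ET days are 8 to 245 or 15 to 252.

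**Size within a row.** The documents give about 750 participants and 40 weeks (280 days). They give no discontinuation rate, so 10% to 30%, spread evenly, is assumed, with every early terminator attending Visit 12 in person.

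- Off-drug values entering a 28-day row: 750 × 0.10 × 28/280 = 7.5, to 750 × 0.30 × 28/280 = 22.5.
- Week 4 receives half of that, because only ET Days 1 to 14 lead into it: 3.75 to 11.25.
- Still on treatment at 10% stopping: 750 − 75 × 56/280 = 735 at Day 56, and 750 − 75 × 252/280 = 682.5 at Day 252.
- Still on treatment at 30% stopping: 750 − 225 × 56/280 = 705 at Day 56, and 750 − 225 × 252/280 = 547.5 at Day 252.
- Share of a row: from 7.5/(735 + 7.5) = 1.0% to 22.5/(547.5 + 22.5) = 3.9%.

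A row mean would move by about 1% to 4% of the difference between the off-drug values and the on-treatment mean. Over all rows the ceiling is 750 × 0.10 × 238/280 = 64 to 750 × 0.30 × 238/280 = 191 participants, before any reduction for remote or missed visits.

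**After capping Weeks 4 to 36 at the last open-label visit.** For ET Days 1 to 283 and offsets of 25, 28 and 31 days, no Visit 12 value meets two of these rows. Each falls only in Safety Follow-up/EOS.

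**The case against.** The best defence is that assignment by study period comes first. The table pairs Weeks 4 to 36 with Visits 2 to 10 and the follow-up row with Visit 12, and the follow-up row is anchored to the participant's own last open-label visit. SAP 4.0 also places table specifications in a separate document that is not available here. This reading is plausible, so a reader who infers that values will be counted twice goes too far: the documents show that precedence is unstated, not that double assignment will occur. But the SAP does not state a period-first step, and the table's first column is labelled as derived. Nor does the term for the day count imply being on drug, since the follow-up row uses it for days after treatment.

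Three further inferences are tempting but unsupported:

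- That the Week 40 cap shows the authors wanted to keep off-drug values out. The last open-label window needs an upper end in any case.
- That all early terminators supply a Visit 12 value. Protocol 8.8 says they should be seen, and its listed reasons include loss to follow-up and withdrawal by the participant. The sponsor's letter of 23 March 2020 made Visit 12 remote for everyone.
- That these values come mostly from people who stopped for tolerability. Adverse event is one of nine listed reasons, and no distribution is given.

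It is also fair to say that a cap at the last open-label visit is not a cap at the last dose. An ET visit held some days after the last dose would still sit in a weekly row.

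**Conclusion.** Wrong as written, minor severity. The overlap follows directly from the stated day ranges. The estimate of roughly 1% to 4% of a row rests on the assumed 10% to 30% even discontinuation and on full in-person attendance at Visit 12. The in-person share is not documented, so the true figure for Visit 12 values is likely lower. Repeat and unscheduled off-drug samples are additional and cannot be counted from the documents.

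A reader might infer that the study's safety conclusions are contaminated. They are not. TEAEs are classified by date (SAP 11.1). PCS determinations use all postbaseline values (SAP 18.3), and the hepatic categories use any qualifying postbaseline value (SAP 11.2). C-SSRS is summarized by period (SAP 11.5), and End of Treatment already stops at the treatment end date. What remains is the by-visit descriptive display of laboratory values and vital signs in a single-arm study.

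**What to change.** In Table 18.1-1, add to each of the Week 4 to Week 36 rows the condition that the assessment is on or before the last open-label visit, as Week 40 already has. Add one sentence: among the visit rows, any assessment after the last open-label visit is assigned only to Safety Follow-up/EOS, and it remains eligible for End of Study.

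The cost is one clause, one sentence and one programming condition, with no new data. Some weekly rows will have a slightly smaller n. The SAP's summary of changes says that the windows were updated to ease ISS preparation, so the same condition should be carried into the ISS window programming.

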18.3 REPEATED OR UNSCHEDULED ASSESSMENTS OF SAFETY PARAMETERS

Baseline is defined as the last assessment made before the first dose of lead-in study treatment. If end-of-study assessments are repeated or if unscheduled visits occur, the last nonmissing postbaseline assessment will be used as the end-of-study assessment for generating summary statistics. However, all postbaseline assessments will be used for PCS value determinations, and all assessments will be presented in the data listings.

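### SAP 18.1 does not require an open-label safety value to follow the first open-label dose, and its End of Study row disagrees with its own note

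*SAP*

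**What the plan says.** SAP 18.1 (Table 18.1-1 and notes) assigns safety assessments to analysis visits.

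- Day 1 is the date of the first dose. Baseline is the lead-in baseline (also SAP 11.0 and 18.3). The first window, Week 4, is "Treatment Day [1, 42" (closed interval).
- The Week 40 window is "Treatment Day [267, the last open-label visit" and the follow-up window is "Treatment Day [the last open-label visit +1, the last study visit". Both are cut by visit.
- The row for the end of the open-label period reads "Last available assessment during open-label treatment period", with no dates. The note adds an upper limit: "End of Treatment is defined as the last available assessment during open-label treatment period, i.e. on or before the treatment end date". SAP 11.4 uses the end of the open-label period for the ECG shift table.
- The End of Study row reads "Last available assessment Day after treatment start date, i.e. occurs at final visit (expected Day 280) or ET". Its note says: "End of Study is defined as the last available assessment during the study, including open-label and safety follow-up period". For repeated or unscheduled assessments, SAP 18.3 says "the last nonmissing postbaseline assessment will be used as the end-of-study assessment for generating summary statistics".

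Protocol 8.4.1 includes Visit 1 in the open-label treatment period and lists dispensing as the last Visit 1 step. Protocol Table 1, footnote a, says procedures already done at lead-in Visit 7 are not repeated at Visit 1.

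**The concern.** This is a single-arm, descriptive safety study, so what a row label means is most of what the reader gets. A row called Week 4 or End of Treatment is read as a value on open-label atogepant. If it can hold a value from before the first open-label dose, it says nothing about that exposure. For a participant who had placebo in the lead-in study (SAP 7.0 lists that group), the value precedes any atogepant at all.

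The effect can run either way. In the descriptive rows, an early stopper can appear unchanged on treatment. In the PCS and hepatic tables, a participant with only a pre-dose value stays in the denominator with no on-treatment data, while an abnormal pre-dose value counts as an event. One route to the latter is a Visit 1 ALT or AST above the Protocol 8.9 withdrawal limit, if the result returns after the first dose.

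The SAP sets start limits elsewhere. The End of Study row requires a day after treatment start, SAP 11.1 summarises only TEAEs starting on or after the first open-label dose date, and the potential Hy's law summary in 11.2 starts at first dose. The weekly windows, End of Treatment, the PCS rules and the remaining hepatic categories have none.

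**Working it through.** **Inputs.** Scheduled days and windows come from SAP Table 18.1-1, and the visit tolerance of ±3 days from Protocol Table 1. ECGs after Visit 1 are at Weeks 12, 24 and 40 only (Protocol 8.4.1.2). Sites should avoid holding Visit 11 earlier than 40 weeks after Day 1 (Protocol 8.4.1.3). Remote visits have no laboratory tests, vital signs or ECG and may continue for up to 8 weeks (SAP Table 4-2).

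**The plan's own figures.** 40 × 7 = 280 (Visit 11) and 44 × 7 = 308 (Visit 12). Window edges are midpoints: (28 + 56)/2 = 42, and so on to (252 + 280)/2 = 266. The weekly grid is consistent.

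**A. No lower limit.**

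1. Treatment days are counted from a date, so a same-day pre-dose value is Day 1.
2. Day 1 lies in the Week 4 window. Neither 18.1 nor 18.3 says which value is used if two fall in one weekly window. If Visit 2 is remote or missed, the Day 1 value may be the only one.
3. Baseline precedes the first lead-in dose, so an extension Visit 1 value is postbaseline. SAP 18.3 uses all postbaseline values for PCS, and the hepatic categories in 11.2 need only one postbaseline value.
4. With no later in-person assessment, the Day 1 value is also the last one in the open-label period.

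How long dosing can run before a later value is due, when ET is not in person:

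| Measure | First scheduled later visit | Latest in-window day | Dosing days before it |
|---|---|---|---|
| Laboratory, vital signs | Day 28 (Visit 2) | 28 + 3 = 31 | 31 − 1 = 30 |
| ECG | Day 84 (Visit 4) | 84 + 3 = 87 | 87 − 1 = 86 |

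On nominal days the figures are 27 and 83. If every visit after Visit 1 is remote, including ET and Visit 12, laboratory values, vital signs and ECG all stay at Day 1 through about 8 × 7 = 56 days.

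**B. The treatment end date.** The term is not defined. SAP 9.1 and 18.4 use the last-dose date, but only for exposure, and 18.2 lists no derived variables. Illustrations:

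| Case | End of Treatment, last-dose cut | End of Treatment, visit cut |
|---|---|---|
| Last dose Day 280, Visit 11 Day 281, laboratory | Day 252 | Day 281 |
| Same, ECG | Day 168 | Day 281 |
| Last dose and Visit 11 both Day 280 | Day 280 | Day 280 |
| Last dose Day 20, ET Day 24, laboratory | Day 1 | Day 24 |
| Last dose Day 60, ET Day 65, ECG | Day 1 | Day 65 |
| Last dose Day 10, no ET | Day 1 | Day 1 |

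Forty weeks after Day 1 is 1 + 280 = Day 281, and the visit window closes at 280 + 3 = Day 283. With a last dose on Day 280 and a last-dose cut, the End of Treatment value is therefore 281 − 252 = 29 to 283 − 252 = 31 days older for laboratory values and vital signs. For ECG it is 281 − 168 = 113 to 283 − 168 = 115 days older. The last table row shows that a visit cut alone does not cure part A.

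**C. End of Study.** The row's Day 280 is the Week 40 visit. The note includes follow-up, which the same table puts at Day 308: 308 − 280 = 28 days. Visit 12 has laboratory tests and vital signs when in person (Protocol 8.4.2.2), none when remote, and no scheduled ECG either way.

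**The case against.** Part A needs several things to be true together. The first dose must fall on the Visit 1 date; one day later, Visit 1 is before Treatment Day 1 and outside the Week 4 window. The instruction to take that dose at the site is in the original protocol of 22 February 2019, which SAP 4.0 names as a basis, but it is absent from the amended section 8.5. The Visit 1 or shared Visit 7 values must enter the extension data, and the SAP is silent on this. For End of Treatment there must also be no later in-person assessment, although Protocol 8.8 says every discontinuer should be seen for final assessments. Those conditions stand and are part of the conclusion. They do not remove the gap, because the remote schedule lets ET pass without laboratory tests, vital signs or ECG.

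A reader might infer that the End of Treatment note flatly conflicts with the Week 40 row and that Visit 11 data are lost. The documents do not support that. These are different analysis visits and may have different upper limits, and a last-dose cut is a legitimate choice for an on-treatment endpoint. If the term means the visit date, or a dose is taken that day, nothing changes. Even under a last-dose cut, the Week 40 row, the PCS, hepatic and QTcF categories and the listings keep the Visit 11/ET data.

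Part C is largely editorial. The row's leading words already admit follow-up, and only the parenthetical day is wrong. Finally, table specifications are in a separate document (SAP 4.0), which may settle the coding.

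**Conclusion.** The main point holds conditionally. SAP 18.1 gives open-label safety values no lower limit at the first open-label dose. Given dosing on the Visit 1 date and inclusion of Visit 1 or shared Visit 7 values, pre-dose values can reach the Week 4 row, the PCS and hepatic counts, End of Treatment and the ECG shift table. It would be too narrow to infer that only the end-of-period rows are exposed.

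The possible lag is up to about 30 dosing days (laboratory, vital signs) or 86 (ECG) for someone who stops before the first later assessment with no in-person ET, and about 56 days for all three if every later visit is remote. The End of Study row is wrong against its note by 28 days, which matters only for laboratory values and vital signs at an in-person Visit 12. The undefined treatment end date is a real ambiguity whose effect ranges from nil to the 29–31 and 113–115 days shown.

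The number of participants affected cannot be derived. TEAE summaries are untouched. The matter is worth settling in the SAP because the rules are explicit and cheap to repair.

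**What to change.** - **Lower limit.** State in SAP 18.1 that any postbaseline open-label value must be taken after the first open-label dose. Apply this to the Week 4 window, End of Treatment, the ECG shift table, and the PCS, hepatic and QTcF categories. Exclude pre-dose Visit 1 values and shared lead-in Visit 7 values. If none remains, the value is missing.
- **One End of Treatment definition.** Use the same rule for End of Treatment and the end of the open-label period, cut at the last open-label visit (Visit 11/ET) as in the neighbouring rows, and refer to it in SAP 11.4. A maximum lag after the last dose is optional and for the sponsor to decide; the documents do not dictate one.
- **End of Study row.** Align it with its note and SAP 18.3 (expected Day 308 where Visit 12 is in person), keeping the requirement that the day be after treatment start.

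The cost is a few sentences in 18.1, matching wording where the PCS, hepatic and QTcF rules are stated, a cross-reference in 11.4, and the corresponding derivation changes. No new data are needed. The price is that a few early stoppers will have no End of Treatment value, and some End of Treatment values will fall shortly after the last dose.
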